8.2.2.2 Factor analysis for adverse events

To identify factors that may be associated with AEs, AEs according to the background factors in section 8.2.1 and special population set in section 5.3 shall be summarized using the number of subjects(n), percentage(%), number of events and the 95% confidence interval of percentage. In addition, to explore the factors that affect the occurrence of AE, univariate analyses based on a Chi-square test or Fisher's exact test(when cells with an expected frequency of less than 5 exceed 20% of total cells) and logistic regression shall be used to assess the impact of each background factor on the AE occurrence and p-value will be provided.

For the final re-examination report, potentially significant factors(p-value<0.05) identified in the univariate analyses will be further explored in a multiple logistic regression model. For final models, odds ratio, 95% confidence interval of odds ratio and p-value will be provided for each factor. If there is no potential significant factor identified in the univariate analyses, multivariate analysis with logistic regression will not be applied.

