5. RATIONALE AND BACKGROUND

Acute lymphoblastic leukemia (ALL) is a rare, serious, and life-threatening condition with a need for improved therapies. Relapsed or refractory B-cell ALL is a fatal disease with a median survival time in adults of only approximately 3-6 months^{1 2}. The age adjusted incidence rate of ALL in the United States is 1.7 per 100,000 individuals per year³, with approximately 6,020 new cases and 1,440 deaths estimated in 2014⁴. While the cure rates and survival outcomes for B-cell ALL have improved during the last several decades, most of the improvements have occurred in younger patients, primarily among children. Recent improvements are largely due to advances in the understanding of the molecular genetics and pathogenesis of B-cell ALL, incorporation of risk-adapted therapy and the advent of targeted agents.

CCI

Before the approval of BESPONSA® in Korea, this non-interventional study is designated as a Post-Marketing Surveillance (PMS) Study and is a commitment to Ministry of Food and Drug Safety (MFDS), as a part of Risk Management Plan (RMP) which is required by MFDS.

PFIZER CONFIDENTIAL

CT24-WI-GL02-RF01 6.0 Non-Interventional Study Protocol Template For Primary Data Collection Study 01-

Aug-2023

Page 10 of 37

The safety and effectiveness information of BESPONSA® will be gathered at minimum 100 subjects administered in the setting of routine practice in Korea during the initial 6 years after the approval.

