7.3.8.1. Definition of adverse events

An adverse event (AE) is any untoward medical occurrence in a patient administered a medicinal product. The event need not necessarily have a causal relationship with the product treatment or usage. Examples of adverse events include but are not limited to:

- Abnormal test findings (see below for circumstances in which an abnormal test finding constitutes an AE);
- Clinically significant symptoms and signs;

PFIZER CONFIDENTIAL

- Changes in physical examination findings;
- Hypersensitivity;
- Progression/worsening of underlying disease;
- Lack of efficacy;
- Drug abuse;
- Drug dependency.

Additionally, for medicinal products, they may include the signs or symptoms resulting from:

- Drug overdose;
- Drug withdrawal;
- Drug misuse;
- Off-label use;
- Drug interactions;
- Extravasation;
- Exposure during pregnancy;
- Exposure during breast feeding;
- Medication error;
- Occupational exposure.

Abnormal test findings

The criteria for determining whether an abnormal objective test finding should be reported as an adverse event are as follows:

- Test result is associated with accompanying symptoms, and/or
- Test result requires additional diagnostic testing or medical/surgical intervention, and/or
- Test result leads to a change in study dosing or discontinuation from the study, significant additional concomitant drug treatment, or other therapy, and/or

PFIZER CONFIDENTIAL

- Test result is considered to be an adverse event by the investigator or sponsor.

Merely repeating an abnormal test, in the absence of any of the above conditions, does not constitute an adverse event. Any abnormal test result that is determined to be an error does not require reporting as an adverse event.

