7.7.1. Safety analysis

- Safety parameter
 - Count and frequency of occurrence of adverse event, serious adverse event, adverse drug reaction or unexpected adverse event by category.
 - Count and frequency of occurrence of adverse events by subject baseline factor and by treatment factor to determine factors affecting the safety.
- Sub-analysis may be performed utilizing factors which are considered to affect safety. If required, chi-square test (χ^2 -test) will be used for subgroup analysis.

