8.1.4 Factorial Analyses

In order to explore the factors associated with the patient's safety and effectiveness profiles, the incidence proportion of AEs and last effectiveness rate will be analyzed by demographics and baseline characteristics factors. The Chi-square test or Fisher's exact test (depending on data counts as appropriate) will be used first to assess the impact for each background factor, and p-value will be outputted. The potentially important factors identified by Chi-square or Fisher's exact test p-values at 0.05 level will be further pooled and tested in a multivariate logistic regression model.

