9. LIST OF TABLES AND TABLE SHELLS

Section I. Analysis for MFDS

Table 1. Patient disposition

Table 2. Demographics and underlying disease information

Table 3. Previous systemic therapy

Table 4. Previous hematopoietic cell transplant

Table 5. Past disease

Table 6. Present disease

Table 7. Veno-occlusive liver disease/Sinusoidal obstruction syndrome(VOD/SOS)

Table 8. Hepatic disorder

Table 9. Renal disorder

Table 10. Allergic history

Table 11. Concomitant medication

Table 12. Administration status of BESPONSA® – Total

Table 13. Summary of Adverse Events

Table 14. Adverse event – AE·ADR

Table 15. Adverse event – Serious AE·ADR

Table 16. Adverse event – Unexpected AE·ADR

Table 17. Adverse event – Unexpected serious AE·ADR

Table 18. Characteristics of adverse events

Table 19. Adverse events by Severity by SOC/PT

Table 20. Adverse events by Action taken by SOC/PT

Table 21. Adverse events by SAE categories by SOC/PT

Table 22. Adverse events by Outcome by SOC/PT

Table 23. Adverse events by Causality to the study drug by SOC/PT

Table 24. Adverse events by Other causality by SOC/PT

Table 25. Categorical factor analysis for adverse events

Table 26. Continuous factor analysis for adverse events

Table 27. Multiple logistic regression for adverse event for the final re-examination

Table 28. Adverse event in elderly(≥65 years) group

Table 29. Adverse event in hepatic disorder group

Table 30. Adverse event in renal disorder group

Table 31. Response evaluations

Table 32. Last effectiveness

Table 33. Categorical factor analysis for last effectiveness

Table 34. Continuous factor analysis for last effectiveness

Table 35. Multiple logistic regression for last effectiveness for the final re-examination

Table 36. Effectiveness(Best overall response)

Table 37. Categorical factor analysis for effectiveness(best overall response)

Table 38. Continuous factor analysis for effectiveness(best overall response)

Table 39. Multiple logistic regression for effectiveness(best overall response) for the final re-examination

Table 40. Non-safety population – AE·ADR

Table 41. Non-safety population – Serious AE·ADR

Table 42. Non-safety population – Unexpected AE·ADR

Table 43. Non-safety population – Unexpected serious AE·ADR

Table 44. Non-PMS Analyses – AE·ADR

Table 45. Non-PMS Analyses – Serious AE·ADR

Table 46. Non-PMS Analyses – Unexpected AE·ADR

Table 47. Non-PMS Analyses – Unexpected serious AE·ADR

Section II. Analysis for publication

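### The only AE factor analysis models any AE, an outcome that can include progression and lack of efficacy, so it is not specific to drug safety and has little power if nearly all patients have an AE

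*SAP*

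**What the plan says.** SAP 8.1.4 states that "the incidence proportion of AEs and last effectiveness rate will be analyzed by demographics and baseline characteristics factors". SAP 8.2.2.2 applies this to safety. Its stated purpose is "to explore the factors that affect the occurrence of AE", by chi-square or Fisher tests and "logistic regression shall be used to assess the impact of each background factor on the AE occurrence and p-value will be provided". Factors with p<0.05 go into a multiple logistic model for the final report. The table list has one such safety model, Table 27: "Multiple logistic regression for adverse event for the final re-examination". Tables 25 and 26 are the matching categorical and continuous factor tables.

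The outcome follows Protocol 7.7.1, which asks for "Count and frequency of occurrence of adverse events by subject baseline factor and by treatment factor to determine factors affecting the safety".

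Protocol 7.3.8.1 includes "Progression/worsening of underlying disease" and "Lack of efficacy" among its examples of AEs. Protocol 7.3.8 has every AE recorded whatever its cause. The restriction on progression in Protocol 7.3.8.2 concerns reporting it as a serious event; it does not remove progression from the AE record.

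SAP 8.2.2 defines an ADR as an AE whose causality is missing or anything other than unlikely. SAP 8.2.2.1 tabulates ADRs, serious events and CTCAE grade by SOC and PT. None of these is carried into 8.2.2.2.

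**The concern.** There are two separate problems.

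**Relevance, at any AE rate.** Refractory, progressive and relapsed disease make up the ineffective category in the effectiveness factor analyses (SAP 8.2.3.3 and 8.2.3.6). If the same course of disease is also recorded as an AE, a baseline factor that predicts treatment failure can produce an association in the safety model. A reader of the re-examination report could not tell that association from an effect on tolerability.

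**Few AE-free patients, depending on the AE rate.** The outcome counts AEs of any grade and any cause, in what Protocol 5 calls "a fatal disease with a median survival time in adults of only approximately 3-6 months". Observation lasts at least 28 days after the last dose and until 180 days after a transplant (Protocol 7.2.3). A high any-AE rate is plausible. If it occurs, the tests and models rest on a handful of AE-free patients, and the SAP has no rule for that case: the multiple model is fitted whenever at least one univariate p-value is below 0.05.

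**Working it through.** **Inputs.** N = 100 (Protocol 7.2.3; SAP 2.1). Screening level p<0.05, taken as two-sided because the SAP does not state sidedness. Test rule from SAP 8.2.2.2: chi-square, or Fisher when more than 20% of cells have an expected count below 5. The documents give no any-AE rate, effect size or power for this analysis, so there is no plan figure to reproduce. Assumed: any-AE rates of 70-98%, odds ratio 3, and factors split 50/50 or 20/80 with the higher risk in the group of 20.

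**Step 1: AE-free patients.** 100 × (1 − rate) gives 30 at 70%, 20 at 80%, 10 at 90%, 5 at 95% and 2 at 98%. The chance that no patient is AE-free, so that nothing can be modelled, is rate^100: 0.98^100 = 0.13 and 0.99^100 = 0.37.

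**Step 2: power.** For each overall rate, group rates p1 and p2 solve p1/(1−p1) = 3 × p2/(1−p2) with (n1·p1 + n2·p2)/100 = rate. Power is the summed binomial probability of all 2×2 tables with p<0.05 under the SAP test rule (chi-square without continuity correction).

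| Any-AE rate | 50/50: p1, p2 | Power | 20/80: p1, p2 | Power |
|---|---|---|---|---|
| 70% | 0.811, 0.589 | 0.69 | 0.854, 0.661 | 0.38 |
| 80% | 0.883, 0.717 | 0.57 | 0.911, 0.772 | 0.19 |
| 90% | 0.946, 0.854 | 0.30 | 0.959, 0.885 | 0.02 |
| 95% | 0.974, 0.926 | 0.06 | 0.980, 0.942 | 0.001 |
| 98% | 0.990, 0.970 | 0.002 | 0.992, 0.977 | 0.002 |

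For a 50/50 factor, odds ratio 2 gives 0.15 at 90% and 0.03 at 95%; odds ratio 4 gives 0.42 and 0.09.

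**Step 3: smallest attainable Fisher p.** In a 50/50 split with all k AE-free patients in one group, p = 2 × C(50,k)/C(100,k).
- k = 3: 0.242; k = 4: 0.117.
- k = 5: 2 × 2,118,760/75,287,520 = 0.056.
- k = 6: 0.027, the first value below 0.05.

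In a 20/80 split the direction matters.
- All AE-free patients in the group of 80 (excess risk in the group of 20): p = 0.58 with 5 and 0.20 with 10. It first falls below 0.05 with 15 (p = 0.037), which corresponds to an any-AE rate of 85%.
- All AE-free patients in the group of 20: two are enough, p = C(20,2)/C(100,2) = 190/4,950 = 0.038.

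**Step 4: would another outcome help?** In a balanced split, power is symmetric about a 50% rate. A 50% outcome gives 0.79 for odds ratio 3 (0.57 in the 20/80 split), while a 10% outcome gives 0.30, the same as a 90% outcome. More power therefore needs an intermediate rate.

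The power figures cover binary factors and the chi-square/Fisher rule only. They do not cover the continuous factors of Table 26.

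**The case against.** A reader might infer that the analysis cannot identify safety factors because nearly every patient will have an AE. The documents do not say so. They give no any-AE rate, and a background median survival is not one. At 70-80% a balanced factor with odds ratio 3 has moderate power, and at higher rates an extreme imbalance in one direction can still be detected, as Step 3 shows.

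A reader might also infer that the protocol's aim is not met. That does not follow, because Protocol 7.7.1 itself specifies AE counts by factor and the SAP delivers them.

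How much progression enters the AE record is not fully clear. Protocol 9.1 and 9.4.3 treat lack of efficacy as a scenario that can be reported without an associated AE. Protocol 7.3.8.2 separately requires the event leading to death from the malignancy to be recorded as an AE, which would be unnecessary if all progression were already recorded. The overlap with effectiveness is therefore possible, and its extent is unknown.

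Other outputs also help. SAP 8.2.2.2 gives event counts by factor, Tables 28-30 give SOC/PT detail in elderly, hepatic and renal patients, and Table 24 shows events attributed to the disease under study. SAP 4 calls the tests exploratory and draws no definite conclusions from p-values.

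These points limit the consequence and rule out the two stronger readings. They do not explain why any AE is the only outcome modelled. Exploratory status governs how a result is read; it does not make the outcome specific to the drug.

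**Conclusion.** The concern holds in two parts.

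The first rests on the text alone. The only modelled safety outcome can be met by progression or lack of efficacy, and the ADR, seriousness and grade data already collected enter no factor analysis. A factor for treatment failure can therefore appear as a safety factor, to an extent that depends on how sites record progression.

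The second is conditional on the assumed rate, odds ratio and splits. At an any-AE rate of about 90% or more, 100 patients give little power (0.30 or less for odds ratio 3). At about 95% or more, power is below 0.10 for odds ratios up to 4 in both splits.

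The change is worth making but is not critical: the study is descriptive and no decision depends on these p-values.

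**What to change.** - Keep the any-AE analysis, which Protocol 7.7.1 asks for.
- Repeat SAP 8.2.2.2 and Tables 25-27 for ADRs and for serious (or grade 3 or higher) AEs.
- In the added analyses, exclude a list of MedDRA terms, fixed before analysis, for progression of the leukemia and lack of efficacy, including fatal malignancy recorded as a serious event. The list is needed for ADRs too, because SAP 7 counts an event with missing causality as related.
- Fit each multiple logistic model only if the smaller of events and non-events is enough for the number of terms, for example 10 per term; otherwise report that outcome descriptively. Under this example, 10 AE-free patients would support one term and 20 would support two.

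The cost is SAP wording, agreement on the term list, and repeat runs of existing programs on data already collected. The downside is more exploratory tables and more unadjusted tests. ADR is broadly defined and may itself be common, so the assured gain is relevance to drug safety, with more power only if the added outcomes have intermediate rates.

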8.2.2.3 Adverse event in special population set

Adverse events reported from special population set in section 5.3 shall be summarized by SOC and PT using the number of subjects(n), percentage(%), number of events and 95% confidence interval of percentage.

8.2.3 Effectiveness Analyses

The effectiveness analyses will be performed for Effectiveness analysis set.

8.2.3.1 Response evaluations

The following response evaluations after each cycle and the final effectiveness evaluation shall be summarized using the number of subjects(n) and percentage (%).

- Response:
 - CR | CRI | Refractory disease | Progressive disease | Relapsed disease
- Effective: CR, CRI
- Ineffective: Refractory disease, Progressive disease, Relapsed disease

8.2.3.2 Last effectiveness

In order to identify last effectiveness of BESPONSA®, the 'effectiveness' is judged as follows based on the final effectiveness evaluation or the last cycle response evaluation(if the final evaluation is missing) and summarized by the number of subjects(n), percentage(%) and 95% confidence interval of percentage.

- Effective: CR, CRI
- Ineffective: Refractory disease, Progressive disease, Relapsed disease

8.2.3.3 Factor analysis of last effectiveness

To identify factors that may be associated with last effectiveness, last effectiveness according to the background factors in section 8.2.1 and special population set in section 5.3 shall be summarized using the number of subjects(n), percentage(%) and 95% confidence interval of percentage. In addition, to explore the factors that affect last effectiveness, univariate analyses based on a Chi-square test or Fisher's exact test (when cells with an expected frequency of less than 5 exceed 20% of total cells) and logistic regression shall be used to assess the impact of each background factor on the last effectiveness and p-value will be provided.

For the final re-examination report, potentially significant factors(p-value<0.05) identified by in the univariate analyses will be further explored and tested in a multiple logistic regression model. For final models, odds ratio, 95% confidence interval of odds ratio and p-value will be provided for each factor. If there is no potential significant factor identified in the univariate analyses, multivariate analysis with logistic regression will not be applied.

PFIZER CONFIDENTIAL

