2.1 STUDY DESIGN

This is a prospective, observational, non-interventional, multi-center study in which subjects will be administered as part of routine practice at Korean health care centers by accredited physicians. The study can be performed in Korean health care centers where BESPONSA® is prescribed to treat the relapsed or refractory B-cell precursor ALL.

All subjects enrolled should meet the usual prescribing criteria for BESPONSA® as per the local product document (LPD) and should be entered into the study at the physician's discretion.

Duration of the Study

According to MFDS re-examination regulation, the re-examination report based on collected data of 6 years must be submitted to MFDS within 3 months after the end of specified re-examination period (from the product approval date to 6 years afterwards).

The data collection period of this study is until the required subject number (100 patients) is collected. The observation period for each subject is from initiating administration of first dose of BESPONSA® to the end of the observation period of the study, which must include at least 28 calendar days following the last administration of a BESPONSA®. In case of patient that Hematopoietic Stem Cell Transplant (HSCT) after administrated BESPONSA®, follow-up until 180 days after transplantation. All the data collected during the observation period should be recorded in the case report form (CRF). In case of an adverse event/safety event recognized after the observation period ends, it should be recorded in the CRF.

Sample Size

CCI

CCI

period. CCI

100 subjects will be collected during re-examination

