4. HYPOTHESES AND DECISION RULES

There is no formal research hypothesis for this study. The purpose of the study is to assess real-life safety and effectiveness of BESPONSA® in Korean adult patients with relapsed or refractory B-cell precursor acute lymphoblastic leukemia (ALL) using the descriptive statistics. For the exploratory analysis, statistical tests may be performed. P-values may be provided, but no definite conclusions will be made based on p-values and no adjustments for multiplicity will be applied.

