8.2.3.6 Factor analysis of effectiveness based on best overall response

To identify factors that may be associated with effectiveness based on best overall response, effectiveness according to the background factors in section 8.2.1 and special population set in section 5.3 shall be summarized using the number of subjects(n), percentage(%) and 95% confidence interval of percentage. In addition, to explore the factors that affect effectiveness, univariate analyses based on a Chi-square test or Fisher's exact test (when cells with an expected frequency of less than 5 exceed 20% of total cells) and logistic regression shall be used to assess the impact of each background factor on the effectiveness and p-value will be provided.

For the final re-examination report, potentially significant factors(p-value<0.05) identified by in the univariate analyses will be further explored and tested in a multiple logistic regression model. For final models, odds ratio, 95% confidence interval of odds ratio and p-value will be provided for each factor. If there is no potential significant factor identified in the univariate analyses, multivariate analysis with logistic regression will not be applied.

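### The final logistic models report ordinary ORs, 95% CIs and p-values only for factors already screened at p<0.05 in the same patients, so these results are post-selection and their nominal levels do not hold

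*SAP*

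**What the plan says.** SAP 8.1.4 sets the general rule: "The potentially important factors identified by Chi-square or Fisher's exact test p-values at 0.05 level will be further pooled and tested" in a multivariate logistic model. SAP 8.2.2.2 (adverse events), 8.2.3.3 (last effectiveness) and 8.2.3.6 (best overall response) repeat it for the final re-examination report.

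- **Screen.** Each background factor in SAP 8.2.1 and each special population in 5.3 is examined by "univariate analyses based on a Chi-square test or Fisher's exact test" and by logistic regression.
- **Entry.** In the words of 8.2.3.3, "potentially significant factors(p-value<0.05) identified by in the univariate analyses will be further explored and tested in a multiple logistic regression model".
- **Output.** "For final models, odds ratio, 95% confidence interval of odds ratio and p-value will be provided for each factor". These results fill Tables 27, 35 and 39.
- **If nothing passes.** "If there is no potential significant factor identified in the univariate analyses, multivariate analysis with logistic regression will not be applied".

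No factor is forced into the model. No separate sample, shrinkage, selection-adjusted interval or label is described.

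For every factor, selected or not, the SAP also plans percentages with 95% CIs and a univariate p-value (Tables 25-26, 33-34 and 37-38). SAP 4 makes the testing exploratory: "no definite conclusions will be made based on p-values and no adjustments for multiplicity will be applied".

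**The concern.** An ordinary Wald interval has 95% coverage when the factor is in the model whatever the data show. Here a factor is in the model because its association in these same patients was already below 0.05. The null hypothesis (adjusted OR of 1) is a proper one. What fails is the reference distribution, which takes no account of the selection. The second step looks like a further test but for a chance finding is largely a repeat of the first.

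Two errors follow in Tables 27, 35 and 39. Factors with no effect that pass the screen tend to keep a CI that excludes 1, and real but weak factors appear with ORs too far from 1. Real factors that miss the threshold get no adjusted estimate and are not adjusted for. Protocol 7.7.1 tabulates adverse events by factor in order to learn what affects safety, so the re-examination report is where such estimates would be read.

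**Working it through.** The documents give no error rate, coverage, response rate or power for the factor analysis, so there is no planned figure to reproduce.

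**Inputs from the documents.** The entry threshold is 0.05. The planned size is 100 patients ("The data collection period of this study is until the required subject number (100 patients) is collected", SAP 2.1). SAP 8.2.1 lists 29 candidate items: 13 + 3 + 8 + 1 + 4 in 8.2.1.1 to 8.2.1.5. Hepatic and renal disorder appear twice, which leaves 27 distinct items.

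**Assumed inputs.** 80-100 evaluable patients; 50-75% effective; 15-27 usable factors, mostly binary; correlation between factors from 0 to 0.6; from none to five real factors with OR 2 to 4.

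**Step 1: how often does a null factor enter?** With k independent null factors, P(at least one passes) = 1 - 0.95^k, and the expected number passing is 0.05k.

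- k = 15: 54%, 0.75 expected
- k = 20: 64%, 1.0 expected
- k = 27: 75%, 1.35 expected

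P(exactly one passes, given any) = k × 0.05 × 0.95^(k-1) / (1 - 0.95^k). This is 66% for k = 16 and 47% for k = 27. In those cases the multiple model is the univariate logistic model refitted.

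**Step 2: what does the final model then say about a null factor?** Simulation of the screen (chi-square, or Fisher under the SAP's expected-count rule), then one logistic model on the same patients:

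| Assumed setting | Selected null factor has p<0.05 again | Nominal 95% CI contains OR 1 |
|---|---|---|
| No real factors, uncorrelated, 16 candidates, N 90-100 | 73-78% | 22-27% |
| No real factors, uncorrelated, 15-27 candidates, N 80-100 | 70-82% | 18-30% |
| No real factors, correlation 0.3 | 53-58% | 42-47% |
| No real factors, correlation 0.6 | 29-32% | 68-71% |
| Three real factors at OR 3, uncorrelated | 59-64% | 36-41% |
| Three real factors at OR 3, correlation 0.3 | 6-12% | 88-94% |
| Fixed model of 3-5 null factors, no screen | 4.3-5.4% | 94.6-95.7% |

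With 16 candidates and no real or correlated factors, a final model is fitted in 51-54% of simulated studies at N = 90 and 75% effective. The sixth row is close to nominal because many null factors there pass the screen through their correlation with real ones, and adjustment then removes them. Real factors alone do not achieve this, as the fifth row shows.

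**Step 3: exaggeration of a weak true effect.** Take N = 90, 75% effective, a factor with 30% prevalence and true OR 0.50.

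- Groups of 27 and 63 patients, with response 0.654 and 0.791. Check: 0.3 × 0.654 + 0.7 × 0.791 = 0.75, and the odds ratio is 0.50.
- SE(log OR) = √[1/(27 × 0.654 × 0.346) + 1/(63 × 0.791 × 0.209)] = 0.51.
- To pass, the estimate must satisfy |log OR| > 1.96 × 0.51 = 1.00, which means an OR below 0.37 (or above 2.7). The true value of 0.50 cannot itself pass.
- True z = ln 0.50 / 0.51 = -1.36, so P(pass) = Φ(-1.96 + 1.36) = 0.27.
- The median OR among passes is about 0.29 by this normal approximation. Full simulation gives 28% selected and a median of 0.24-0.27. A fixed five-factor model gives a median of 0.48.
- Coverage of the true OR among passes is about (0.274 - 0.025)/0.274 = 91%. Simulation gives 88-92%.

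So the severe loss of coverage concerns null factors. For a weak real factor the main fault is the inflated estimate.

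**Step 4: what share of significant rows is null?** With 20 uncorrelated candidates and N = 100:

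- one real factor: 72% (OR 2), 54% (OR 3)
- two: 55% (OR 2), 35% (OR 3)
- three: 25% (OR 3)
- five: 11% (OR 4)

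**The case against.** The strongest reply is that SAP 4 already declares the tests exploratory, rests no definite conclusion on p-values and disclaims multiplicity control, and that the SAP's language is about exploring potential factors. This stands as a limit on the consequence. It does not reach the ORs and CIs, which are read as estimates and are biased or miscalibrated whatever is concluded from the p-values.

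A second reply is that the multiple model tests an adjusted association and so is more than a repeat. That is right when several correlated factors enter together with real predictors, and coverage then approaches nominal. The SAP 8.2.1 items do overlap (age and elderly; height, weight and body surface area), so the uncorrelated figures are the unfavourable end of the range. When one factor enters alone, there is nothing to adjust for.

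A third reply is that unselected summaries are already planned for every factor. That stands: six of the nine factor tables for these outcomes are unscreened. Only table titles are visible, so it cannot be excluded that the shells already hold univariate ORs with CIs; the text promises ORs only for final models.

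A reader might also infer that most factors reported as significant will have no effect. The documents do not support that. The share of null rows ran from 11% to 72% once real factors were present, and nothing in the plan places this study within that range.

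**Conclusion.** The plan is wrong as written on a limited point. The ORs, 95% CIs and p-values in Tables 27, 35 and 39 are conditional on passing a screen in the same data, and neither the method nor any label reflects this. For a null factor, coverage of the nominal 95% CI ranges from about 20-30% (uncorrelated, no real effects) through about 70% (correlation 0.6) to about 90% (three real factors at OR 3 with correlation 0.3). A weak true OR of 0.50 is reported at a median of about 0.24-0.27. Every one of these sizes rests on assumed sample size, response rate, prevalences and correlations. The simulations used a generic binary outcome with 50-75% effective, so they carry over to adverse-event occurrence only if its frequency is in that region.

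It would be too strong to say that the models test the wrong null hypothesis or that they chiefly report ineffective factors. SAP 4 reduces what will be claimed from the p-values but leaves the estimates and intervals uncorrected.

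**What to change.** In SAP 8.1.4, 8.2.2.2, 8.2.3.3 and 8.2.3.6:

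1. Remove the p<0.05 entry rule and the clause that cancels the model when nothing passes.
2. For each outcome, list one short model and fit it whatever the univariate results. Use only factors known at first dose. SAP 8.2.1 also lists total cycles, total dose and concomitant medication, which arise during treatment. Age, Philadelphia status, disease status, previous transplant and hepatic disorder are examples of suitable candidates.
3. Choose the list on clinical grounds without reference to accumulated outcome data, and say so. The SAP follows protocol Amendment 4 of November 2023, by which date six periodic submissions were scheduled to have been made (SAP 3).
4. Keep each model to about five parameters or fewer, governed by the smaller outcome category. With 90 evaluable and an assumed 75% effective, 0.25 × 90 = 22.5 patients are non-effective, or 4.5 per parameter with five parameters, so Firth's penalty is advisable. If nearly all or very few patients have an adverse event, that model must be shorter.
5. In Tables 25-26, 33-34 and 37-38, give the univariate OR with 95% CI for every factor.
6. If the screened model is kept as a supplement, label its ORs, CIs and p-values as post-selection and exploratory.

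The cost is SAP wording and small changes to nine tables, with no new data. The downside is that factors outside the list get univariate estimates only.
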